If disease progression is indicated clinically or by local radiologic assessment according to RECIST 1.1 at or after Week 13 but before Week 25, the Investigator may request a central review for evaluation of disease progression. If a central reading confirms RECIST 1.1-defined disease progression, treatment assignment will be unblinded, and subjects receiving placebo will be eligible for early entry into Part 2 of the study. Effective 30 Sep 2016, subjects receiving placebo will be discontinued instead of being eligible to enter Part 2. Subjects receiving pexidartinib will be discontinued from the study unless the Investigator and the Sponsor's Medical Monitor judge that the subject would potentially benefit from continued treatment with pexidartinib. During Parts 1 & 2 of the protocol, the Investigator may request an expedited central review of a scan locally assessed as disease progression according to RECIST 1.1.

All subjects in Part 2 will continue to receive open-label pexidartinib until all subjects have either reached at least the Week 49 visit (ie, an additional 24 weeks of open-label pexidartinib treatment beyond the placebo-controlled phase) or withdrawn from the trial. Those subjects who complete Part 2 will be eligible to continue for longer efficacy and

safety follow-up or to enter a separate protocol to continue receiving pexidartinib.

For statistical analysis of endpoints at the end of Part 1, a clinical data cut-off date will be defined for the point when all randomized subjects complete or are discontinued from Part 1 with appropriate End of Part 1 follow-up. All data up to this date will be cleaned. Unblinding of database will be performed to facilitate the data analyses, including the data from the double-blind Part 1 and available data from Part 2. Such unblinding is only intended for the sponsor and the Contract Research Organization. Subjects who entered Part 2 may continue to receive open-label pexidartinib treatment. Updated analysis of Part 2 data only, in the form of summary and descriptive statistics, will be performed at the end of the trial. Additional updates between the above-mentioned cut-off and end of the trial may also be performed.

A range-of-motion assessment in the affected joint or tumor location will be performed by an independent and blinded third party assessor at specified time points. PRO instruments will also be completed at specified time points.

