Ongoing safety will be monitored by an independent DMC according to a separate charter.

Subjects who end their study participation early with no radiologic disease progression will undergo: (i) the 28 Day Post-treatment Visit assessment *with* an MRI 28 ± 7 days after their last dose of study treatment; and (ii) a final MRI 12 weeks ± 7 days after their last dose of study treatment or before any new PVNS therapy, including surgery, whichever occurs first (the "Part 1 End-of-Study/12 Week Post-Treatment Visit"). After completion of the end of Part 1 assessments (Part 1 Completion visit/Early Termination visit), subjects who wish to continue onto the open label part of this study (Part 2) will be unblinded and those on placebo will be discontinued; subjects on pexidartinib in Part 1 may continue into Part 2 to continue to receive pexidartinib. Subjects who complete Part 2 and choose to enter a separate protocol to continue receiving pexidartinib will not have the Post-treatment and End-of-Study Visit assessments. Subjects who terminate the study with radiologic disease progression will undergo the Post-treatment Visit assessment *without* an MRI 28 ± 7 days after their last dose of study treatment or before any new PVNS therapy, including surgery, whichever occurs first.

Subjects are allowed to undergo surgical resection of their tumor after the completion of Part 1. For subjects who undergo surgical resection within 12 weeks after their last dose of study treatment, they will not have the End-of-Study Visit assessments but will follow a separate visit schedule after the decision of surgery is made. The surgery is recommended to be performed 1-3 weeks after the last dose of study

	
treatment. Details of the surgery and its short and long term outcome will be collected. Data collection for the surgery and its outcome may continue in a separate protocol.

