All MRI scans will be assessed by central readers blinded to treatment assignment and other clinical study data during both Parts 1 and 2 of the study, according to procedures outlined in a separate Imaging Independent Review Charter. The MRI report will not be provided in real-time unless requested by the Investigator. Results of the baseline MRI scan will be used to qualify a candidate. During Part 2, if indicated, Investigators should request confirmation of radiologic disease progression by central read. Otherwise, central reads of MRI scans may be performed during or after the subject has completed the study. The MRI scan for subjects who undergo surgical resection will be performed 4 months after surgery. Details of MRI requirements and data collection will be described in the MRI Procedure Manual.

A range-of-motion assessment in the affected joint or tumor location will be performed by an independent and blinded third party assessor at specified time points. The BPI Worst Pain NRS item, physical function items from the PROMIS item bank (PROMIS Physical Function Scale), and other PRO measures will be administered according to the Study Reference Manual.

[figure not shown]
For statistical analysis of endpoints at the end of Part 1, a clinical data cut-off date will be defined for the point when all randomized subjects complete or are discontinued from Part 1 with appropriate End of Part 1 follow-up. All data up to this date will be cleaned and locked. Afterwards, unblinding of database will be performed to facilitate the data analyses, including the data from the double-blind Part 1 and available data from Part 2. Such unblinding is only intended for the sponsor and the Contract Research Organization. Subjects who entered Part 2

may continue to receive open-label pexidartinib treatment. Updated analysis of Part 2 data only, in the form of summary and descriptive statistics, will be performed at the end of the trial. Additional updates between the above-mentioned cut-off and end of the trial may also be performed.

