5.6. Blinding and Unblinding

Part 1 will be the placebo-controlled double-blind phase of the study where treatment assignment will remain unknown to the study subjects, Investigators, study site personnel, safety laboratory personnel, central imaging readers, and representatives of Daiichi Sankyo involved in the conduct and/or management of the trial. Pexidartinib and placebo capsules will be identical in appearance. All study treatment (pexidartinib or placebo) will be labeled with the study number, a unique number, and any additional information required in accordance with government regulations. Further details are contained in the separate Pharmacy Manual.

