For statistical analysis of endpoints at the end of Part 1, a clinical data cut-off date will be defined for the point when all randomized subjects complete or are discontinued from Part 1 with appropriate End of Part 1 follow-up. All data up to this date will be cleaned and locked. Afterwards, unblinding of database will be performed to facilitate the data analyses, including the data from the double-blind Part 1 and available data from Part 2. Such unblinding is only intended for the sponsor and the Contract Research Organization. Subjects who entered Part 2 may continue to receive open-label pexidartinib treatment. Updated analysis of Part 2 data only, in the form of summary and descriptive statistics, will be performed at the end of the trial. Additional updates between the above-mentioned cut-off and end of the trial may also be performed.

5.6.1.3. Unblinding at the End of Part 1

As of 30 Sep 2016, subjects on placebo in Part 1 are no longer allowed to enter Part 2 to receive open-label pexidartinib. After completion of the end of Part 1 assessments (Part 1 Completion visit/Early Termination visit), subjects who wish to continue onto the open label part of this study (Part 2) will be unblinded and those on placebo will be discontinued; subjects on pexidartinib in Part 1 may continue into Part 2 to continue to receive pexidartinib. (Detailed instructions will be provided separately.)

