9.2.4. Causality Assessment

The Investigator should assess causal relationship between an adverse event and the study treatment on the basis of his/her clinical judgment and the following definitions. The causality assessment should be made based on the available information and can be updated as new information becomes available.

- Related:
 - The AE follows a reasonable temporal sequence from study treatment administration, and cannot be reasonably explained by the subject’s clinical state or other factors (eg, disease under study, concurrent diseases, and concomitant medications).
 - The AE follows a reasonable temporal sequence from study treatment administration, and is a known reaction to the drug under study or its chemical group, or is predicted by known pharmacology.
- Not Related:
 - The AE does not follow a reasonable sequence from study product administration, or can be reasonably explained by the subject’s clinical state or other factors (eg, disease under study, concurrent diseases, and concomitant medications).

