9.3. Serious Adverse Event Reporting Procedure for Investigators

9.3.1. Reporting by Investigators

All AEs and SAEs will be reported in the eCRF.

The following types of events should also be reported on the Daiichi Sankyo Serious Adverse Event Report (SAVER) Form within 24 hours of awareness:

- SAEs (Section [9.2.2](#))
- Hepatic events meeting combination abnormalities [ALT or AST $\geq 3 \times$ ULN with simultaneous total bilirubin $\geq 2 \times$ ULN] (potential Hy's Law case), both serious and non-serious

All AEs (serious and non-serious) must be reported with Investigator's assessment of the event's seriousness, severity, and causality to the blinded study treatment. A detailed narrative summarizing the course of the event, including its evaluation, treatment, and outcome should be provided. Specific or estimated dates of event onset, treatment, and resolution should be included when available. Medical history, concomitant medications, and laboratory data that are relevant to the event should also be summarized in the narrative. For fatal events, the narrative should

state whether an autopsy was or will be performed, and include the results if available. Source documents will be retained in site's files and should not be submitted to the Sponsor for SAE reporting purposes.

Urgent safety queries must be followed up and addressed promptly. Follow-up information and response to non-urgent safety queries should be combined for reporting via eCRF to provide the most complete data possible within each follow-up.

Please call the local SAE Hotline or your study monitor for any questions on SAE reporting (see Section [10.1.2.2](#)).

9.3.2. Notifying Regulatory Authorities, Investigators, and Institutional Review Boards/Institutional Ethics Committees

The Sponsor and/or designee will inform Investigators, IRBs/IECs, and regulatory authorities of any suspected unexpected serious adverse reactions (SUSARs) occurring in other study centers or other Daiichi Sankyo studies of the investigational product, as appropriate per local reporting requirements.

In the US, upon receipt of the Sponsor's notification of SUSARs that occurred with the investigational product, unless delegated to the Sponsor, it is the Investigator's responsibility to inform the IRB per the Sponsor's instruction.

In the European Economic Area member states, it is the Sponsor's responsibility to report SUSARs to all IECs.

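### From 30 Sep 2016, subjects seeking Part 2 are unblinded one at a time before Part 1 data are locked, so late or revised causality ratings and per-protocol decisions can be made knowing the arm

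*Combined protocol and SAP*

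**What the plan says.** Section 5.6.1.3 gives the rule and its date: "As of 30 Sep 2016, subjects on placebo in Part 1 are no longer allowed to enter Part 2 to receive open-label pexidartinib". The timing is "After completion of the end of Part 1 assessments (Part 1 Completion visit/Early Termination visit"), at which point "subjects who wish to continue onto the open label part of this study (Part 2) will be unblinded and those on placebo will be discontinued". The same rule appears in the Synopsis and in Sections 1.6, 3.1 and 15.2.16. The code is thus released subject by subject.

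The Part 1 database follows a different clock. Section 3.1 sets a single cut-off, when all randomized subjects have completed or left Part 1, and continues: "All data up to this date will be cleaned and locked. Afterwards, unblinding of database will be performed to facilitate the data analyses". Section 5.6.1.2 repeats this. The Synopsis has the same sentence without the lock: "All data up to this date will be cleaned. Unblinding of database will be performed to facilitate the data analyses".

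On blinding, Section 5.6 describes Part 1 as the phase "where treatment assignment will remain unknown to the study subjects, Investigators, study site personnel", and also covers the sponsor's trial staff. Section 9.3.1 asks investigators to rate "causality to the blinded study treatment". Section 9.2.4 adds: "The causality assessment should be made based on the available information and can be updated as new information becomes available".

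Section 7.10 tabulates treatment-emergent events by relationship and severity for each treatment group, with Part 1 pexidartinib and Part 1 placebo as separate data sets. Section 7.2 defines the Per-protocol Set by the absence of major eligibility or protocol violations and by at least 70% compliance. It names no decision date, decision maker or blinded review.

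**The concern.** Before 30 Sep 2016, completers from either arm could advance to open-label drug, so entry into Part 2 did not reveal the arm. Under the current rule, entry itself identifies pexidartinib, and discontinuation at that point identifies placebo. Section 15.3 also gives known pexidartinib subjects a reduced visit schedule. The sponsor sees all data as they are entered (Section 11.2).

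No visible provision freezes a subject's Part 1 record before that subject's code is released. The record stays open to queries and updates until the last randomized subject finishes Part 1. Events unresolved at Week 25 must be followed (Sections 6.4.17 and 9.1) by an investigator who now knows the arm. Under Section 9.2.4, one route to a rating of related is that the event is already recognised for the drug, so the arm bears directly on the rating. Section 1.6 lists the unblinding rule alongside a duty to tell investigators of new safety information, which makes a second look at causality more plausible.

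What is at stake is the by-relationship part of the controlled Part 1 safety comparison and, less so, membership of the Per-protocol Set.

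**Working it through.** The plan gives no figure on this point. Its one design figure, 90% power at 63 per arm for 10% versus 35%, reproduces (exact Fisher power 90.6%) and does not bear on the question. The check is a comparison of provisions in time order for one subject.

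1. **Week 25 visit, before code release.** Adverse-event assessment is part of this visit (Sections 15.2.16 and 15.3.1). At each visit the investigator must rate seriousness, severity and causality and sign the source record (Section 9.1). Ratings made here are blind.
2. **Code release.** This follows the assessments (Section 5.6.1.3). No sign-off or freeze of the eCRF entries is required first.
3. **Interval to the common cut-off.** Ongoing events are followed, queries are answered and causality may be updated (Sections 9.1, 11.4 and 9.2.4). Entries made or changed here can be made with the arm known.
4. **Lock.** Part 1 data are cleaned and locked together (Section 3.1).

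Step 3 does not fit the blinding described in Section 5.6 or the blinded causality rating in Section 9.3.1.

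**How exposed each Part 1 result is**

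| Result | Exposed by this route? |
|---|---|
| Primary RECIST response and TVS response | No: central readers stay blinded in both parts (Sections 2.2.1 and 3.1) |
| Range of motion | No: blinded third party, measured before code release (Sections 6.4.4 and 15.2.16) |
| PROMIS, stiffness, BPI-30 | Not materially: subject diary, completed before code release |
| All-causality TEAEs and SAEs by arm | Not materially: causality is not used (Sections 7.10 and 7.10.1) |
| Laboratory shift tables | Not materially: built from measured values (Section 7.10.2) |
| TEAEs by severity | Slightly: graded by CTCAE (Sections 7.10.1 and 9.2.3) |
| TEAEs by relationship | Yes, for late, queried or revised entries |
| Per-protocol membership | Yes for the major-violation judgement; the 70% limb is numeric |

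**Number affected.** The documents do not say how many subjects reached the end of Part 1 on or after 30 Sep 2016 and asked for Part 2. It could be anything from 0 to 126.

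**Illustration only.** Let s be the share of placebo subjects in that group (0 to 1). Let q be the share with an event called related while blinded (assumed 30% to 60%). Let r be the share of those whose related events are all re-rated as not related after unblinding (assumed 10% to 30%). Take q and r to be the same in subjects seeking Part 2 as in the whole arm. The fall in the placebo related-event rate is q × r × s:

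- low: 0.30 × 0.10 × s = 0.03s
- high: 0.60 × 0.30 × s = 0.18s
- example with s = 0.5: 0.50 × 0.20 × 0.5 = 0.05, or 5 percentage points (0.05 × 63 ≈ 3 placebo subjects)

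As s runs from 0 to 1, the span is 0 to 18 points. None of q, r or s comes from the documents, and re-rating could also go the other way.

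**The case against.** The strongest reply is that ratings are due before the code is released. Section 9.1 requires a signed assessment at each visit, SAEs are reported within 24 hours (Section 9.3.1), deviations are notified on an expedited basis (Section 6.5), and every eCRF change carries user, date and time (Section 11.3). This stands, and it confines the point to late, queried or revised entries.

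A second reply is that the clean-and-lock order governs release of the database to the sponsor and CRO for analysis, whereas the Week 25 rule is a subject-level release that followed a DMC recommendation. A reader might infer that the rule breaches the Section 3.1 order. The documents do not support that, because that order was never stated as a safeguard against individual release. Individual unblinding before lock already existed for emergencies and for centrally confirmed progression (Sections 5.6.1.1 and 5.6.1.2). For the same reason, subjects seeking Part 2 are not the only ones unblinded before lock, although Section 4.2.2 keeps other early discontinuers blinded.

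Third, Section 5.6.1.3 says detailed instructions are provided separately, and Sections 7.4 and 7.6.2 defer details to the SAP. A sign-off step or a blinded per-protocol review could be in that material, which was not seen. The point rests on the silence of the visible text.

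Fourth, the Per-protocol Set supports sensitivity analyses only (Section 7.6.2). This also stands.

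**Conclusion.** The gap is real but narrow. For subjects who ended Part 1 on or after 30 Sep 2016 and asked for Part 2, the text permits Part 1 causality entries, and less so severity entries, to be entered late or revised with the arm known. It permits the same for judgements of major violations.

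A reader might infer that the controlled safety comparison as a whole is compromised. It is not: Part 1 also has all-causality TEAE and SAE tables and laboratory, vital-sign and ECG comparisons by arm, none of which uses the causality rating. A reader might also infer that bias occurred or that its size is known. The documents show only what is permitted. The 0 to 18 point span rests wholly on assumed rates and an unstated number of subjects. The primary and gated analyses are not materially exposed.

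The conclusion assumes that the unseen instructions and SAP details contain no equivalent safeguard. Priority: low, a cheap improvement.

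**What to change.** In Section 5.6.1.3, require the investigator to sign off the subject's Part 1 causality, severity and deviation entries before IXRS releases the code. Flag any later change from the existing audit trail. Add a sensitivity version of the Part 1 TEAE-by-relationship table on the pre-release values. Keep the final causality in the main table, because Section 9.2.4 allows legitimate updates, for example from the liver work-up in Table 5.2. Classify major violations before code release, or have this done by staff without access to arm or Part 2 status.

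The text is Version 10.0 of 22 Jan 2020, more than three years after the rule took effect, so Part 1 may be complete. A prospective sign-off would then apply to nobody, but the sensitivity table can still be run retrospectively from the time-stamped audit trail and would show whether ratings moved after unblinding. Aligning the Synopsis with Section 3.1 on locking is an editorial correction.

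The cost is a short wait for sign-off before code release and one extra table.

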1. INTRODUCTION AND BACKGROUND INFORMATION

A comprehensive review of pexidartinib (PLX3397) is contained in the Investigator's Brochure (IB). Investigators should review the IB prior to initiating this study. A brief review of pexidartinib is provided here.

1.1. Scientific Background

1.1.1. Pigmented Villonodular Synovitis and Giant Cell Tumors of the Tendon Sheath

Pigmented villonodular synovitis (PVNS) and giant cell tumors of the tendon sheath (GCT-TS) are members of a single condition referred to as “tenosynovial giant cell tumour (TGCT), localized and diffuse type” and have a common pathogenesis¹. They are rare proliferative neoplasms involving the synovium and tendon sheaths that typically present in young and middle-aged adults of both sexes. PVNS and GCT-TS are usually monoarticular processes that involve the bone, soft tissue, synovium, or tendon sheath of small or large joints. Symptoms initially may be minimal due to the slowly progressive nature of the disease, but as the tumor mass grows and gradually expands within the fixed confines of the intra-articular space (and surrounding tissue); symptoms such as pain, stiffness, swelling, and limitation in range of motion (ROM) can become severe and result in marked functional limitation. The diagnosis of PVNS is definitively made from pathologic evaluation; however, features highly suggestive of the disease may be found on radiologic imaging, including computed tomography and magnetic resonance imaging (MRI).

PVNS and GCT-TS tumors predominantly consist of mononuclear and multinucleated giant cells. In both diseases, expansion of the tumor mass appears to be driven by the presence of abundant Colony stimulating factor 1 (CSF-1) expressed by a subset of cells within the tumor and often associated with genetic translocations linking the collagen 6A3 gene (on 2q35) with the CSF-1 gene (on 1p13). The majority of cells in the tumor mass are non-neoplastic inflammatory cells that do not express CSF-1 but are attracted to the tumor site because of their expression of the receptor, Colony stimulating factor 1 (CSF1R).

Both PVNS and GCT-TS are rare, with an estimated annual incidence of 1.8 cases per million and 9.2 cases per million, respectively, in the US.² In a review of a Scottish hospital case series, Monaghan and coworkers suggested an incidence of 0.2 cases of GCT-TS per 10,000 in the EU.³ Similarly, Ushijima et al.⁴ described an incidence of 0.25 cases per 10,000 in Kyushu, Japan, while a paired study suggested a PVNS incidence of 0.06 per 10,000.⁵ Patients are commonly diagnosed in their 20s to 50s, and the disease affects men and women equally.^{2,6}

PVNS and GCT-TS are challenging diseases to manage. The current standard of care is surgical resection of the tumor as completely as possible in order to: (1) reduce pain, stiffness, and joint destruction caused by the disease process; (2) improve function; and (3) minimize the risk of recurrence. Patient outcome following surgery depends on multiple factors, including the location and extent of disease, thorough diagnostic evaluation, and the technical skill of the surgeon. The overall recurrence rate for patients with focal localized disease is low, ranging from 0% to 6%; however, in patients with diffuse forms of the disease, recurrence is considerably more common, estimated to be in the range of 40%. Diffuse disease carries a significant risk of

multiple recurrence, and affected patients often have more extensive involvement and a poorer likelihood of success with surgery. Surgical resection may involve removal of major tendons, neurovascular structures, or limbs, leading to significant postsurgical morbidity.

Currently, there are no systemic agents approved for the treatment of PVNS or GCT-TS. Products that are being evaluated in PVNS and GCT-TS include: imatinib (Gleevec)^{7,8} a multi-kinase inhibitor that targets Bcr-Abl tyrosine kinase yet also shows activity against CSF1R; nilotinib (Tasigna), a second-generation drug based on imatinib⁹, a macrophage colony stimulating factor antibody; and a humanized monoclonal antibody that targets CSF1R.¹⁰

